Study Design:	
Phase 1 prospective non-randomised safety cohort study with all patients recruited from a single UK site (Oxford). The study has an open label design with all participants receiving ThermoDox® and FUS. The study will run in two parts. Part I is required to identify optimal FUS exposure parameters using real time thermometry data from an implanted thermometry device, such as a thermistor. Part II does not require implantation of thermometry device and is designed to more accurately reflect how the therapy would be implemented in clinical practice. All evaluable participants from both Part I and Part II will be included in the endpoint analysis.
 
Part I
 
For each participant, a single liver tumour will receive the intervention and follow-up imaging. The ability to achieve targeted release of doxorubicin from ThermoDox® at the tumour site will be determined using three tumour biopsies with corresponding peripheral blood samples taken during intervention and/or using a radiological method (MR-Spectroscopy).
 
Part II
 
For each participant, a single liver tumour will receive the intervention and follow-up imaging.. The optimal FUS exposure parameters determined in Part I will be selected for Part II interventions, accounting for differences in propagation path length identified in the Ultrasound Session. The ability to achieve targeted release of doxorubicin from ThermoDox® at the tumour site will be determined using the same methods as for Part I, with the exception of requiring only two tumour biopsies.
 
In the 30 days following intervention, both Part I and II participants will be followed up with a maximum of two CTs, two PET-CTs and three MRI/MR-Spectroscopy scans. There is however built in flexibility for the scans to be performed at different timepoints up to 60 days post intervention should the patient provide this optional consent and not have started another treatment. If available, other non-FUS control tumour(s) in the liver exposed to ThermoDox® alone will be selected as controls against which radiological response in the FUS-targeted tumour (target tumour) will be compared.
 
Detailed criteria for evaluation of efficacy and safety are described in subsequent sections.

Patient Numbers:	A maximum of 28 evaluable participants will be recruited to the study overall.

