2 STUDY DESIGN

Phase 1 prospective non-randomised open label single site study to determine whether targeted release of doxorubicin from ThermoDox® ('drug') using mild hyperthermia generated non-invasively by FUS is possible in cancer patients. All participants will receive ThermoDox® and FUS.

The study will run in two parts. Part I will identify optimal FUS exposure parameters for a range of patient BMIs and tumour locations within the liver using real time thermometry data from an implanted thermometry device, such as a thermistor or thermocouple. After at least 5 participants have had the intervention using real-time thermometry, data will be reviewed by the Trial Management Group (TMG) to confirm readiness to proceed without real-time thermometry (Part II). Part II, which does not require implantation of a thermometry device, is designed to reflect how the therapy would be implemented in clinical practice. All evaluable participants from both Part I and Part II will be included in the endpoint analysis.

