To assess the safety of FUS-induced mild hyperthermia for drug delivery	1. Persistence of cell viability stain or percentage of cell or tissue necrosis under 30% following FUS exposure, as assessed by cytological or histological	1. Cytological or histological analysis of biopsy samples processed within 96hr of intervention†

	methods ¹⁶ ‡,§ 2. Adverse events deemed related to FUS up to 30 days post-intervention	2. Adverse event recording for 30 days post-intervention
To assess the local and systemic cytotoxic effects of ThermoDox® in this setting	1. Significant bone marrow suppression, deranged liver function and liver toxicity 2. Adverse events deemed related to ThermoDox® up to 30 days post-intervention	1. Grade 3 and 4 laboratory results from blood tests at Day 1 and Day 15 post intervention 2. Adverse event recording for 30 days post-intervention

Table 2: Secondary Objectives and Endpoints for Parts I & II of the TARDOX Study

Regarding participants for which doxorubicin has been released by optimal FUS exposure parameters:

Tertiary (Exploratory) Objectives	Tertiary (Exploratory) Endpoints	How and when data is captured
1. To establish the validity of other minimally-invasive and non-invasive methods of evaluating intratumoural uptake of doxorubicin as an alternative to that used in primary endpoint	Combined analysis of relevant end points to establish most effective alternative analytical method(s) for quantifying drug release	See below
a. Fluorescence microscopy of biopsy	Released biopsy samples exhibiting regions of nuclear or background fluorescence levels at least twice that of a suitable control, as assessed by fluorescence microscopy ‡,§	Microscopic analysis of biopsy samples processed within 96hr of intervention†
b. MR-Spectroscopy	Liver MRI/MR-Spectroscopy indicating ¹⁷ targeted delivery of doxorubicin to the tumour by demonstrating a statistically significant increase in the tumour:background ratio of signal intensity following intervention compared to baseline	MRI/MR-Spectroscopy signal within 36 hours of intervention
c. Plasma pharmacokinetics	A statistically significant decrease in total doxorubicin plasma levels over time-matched clearance levels, following HIFU-induced release	Analytical chemistry of plasma samples processed within 12hr of intervention†

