5.2 Evaluations during the intervention (d-1 to d2)

Evaluations on day -1 (pre-Intervention day)

- Dose of oral dexamethasone given as pre-medication (section 5.5.2 & 9.3)
- Baseline scans (Usually on d-1 but may be performed from day -7 to day 1 provided before intervention):
 - Liver MRI/MR -Spectroscopy
 - Liver pCT

- Whole body FDG PET-CT

Evaluations on day 1 (intervention day)

- Confirm d-1 pre-medications were given.
- Day 1 pre-medications given
- Confirmatory portable ultrasound to confirm tumour location before patient anaesthetised
- General anaesthetic start and finish time
- Dose of ThermoDox® administered, start and finish time
- Start and finish time of final FUS exposure and FUS parameters
- Thermometry data (Part I only)
- Bloods samples for pharmacokinetics (Pre-Treatment, Unreleased and Released plasma samples)
- Biopsy samples for assay quantification \pm microscopy:
 - Part I: Pre-Treatment, Unreleased, Released
 - Part II: Released
- Adverse event monitoring

Evaluations on day 2 (recovery day)

- Physical exam
- Vital signs: Temperature, resting pulse and blood pressure (BP) after participant has been in a sitting position for at least five minutes
- Full Blood Count (FBC); including Haemoglobin (Hb), white blood cells (WBC) with differential count (neutrophils and lymphocytes), and platelets
- Biochemical profile; including sodium, potassium, calcium, phosphate, urea, creatinine
- Liver profile; including total protein, albumin, bilirubin, ALP, AST and/or ALT and LDH
- Post-treatment Liver MRI/MR-Spectroscopy (within 36 hours, and ideally within 24 hours, of intervention¹⁸)
- Adverse event monitoring

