- A Pre-Treatment Biopsy of the tumour is taken via the co-axial needle, and used as a baseline prior to any intervention, along with the Pre-Treatment blood sample.
- A clinically approved thermometry device is then positioned through the co-axial needle to the target area and is used to obtain real-time thermometry measurements during the FUS exposure.
- The HIFU therapeutic device is aligned to the thermometry device using short test exposures of FUS.

- The tumour area is then exposed to varied and considered FUS parameters (section 5.4.3) until the thermometry confirms that the target range of mild hyperthermia has been achieved within the tumour(*).
- In addition to the FUS exposure parameters (power (watts), duty cycle, duration of treatment) and associated thermometry data, the location of tumour (liver segment) and patient BMI will be recorded for each intervention.
- The thermometry device is then replaced and a cool-down period allows the tumour to return to body temperature.
- Once the tumour has returned to normothermia, the prescribed dose of ThermoDox® is infused over a duration of 30 minutes.
- A second Unreleased Drug Biopsy of the target area is then taken via the coaxial needle (Note: ThermoDox® is circulating at this point, but not yet activated). The corresponding Unreleased Drug blood sample is also taken at this stage for pharmacokinetic analysis within 15 minutes of infusion end.
- The tumour area is then re-exposed to FUS using the exposure parameters identified earlier as being suitable to generate mild hyperthermia within the tumour. During this second FUS exposure, ThermoDox® is circulating between therapeutic and peak levels.
- After completion of the final FUS exposure, a final Released Drug biopsy is taken via the co-axial needle with the corresponding Released Drug blood sample.
- Before removing the coaxial needle, a Gelfoam® (or equivalent) plug embolization of the needle track is applied through the needle to minimise bleeding risk [47].

*Note that with increasing experience, the study team may elect to omit the step of pre-heating the tumour prior to drug delivery (1st FUS exposure) and drug infusion may be commenced shortly after alignment.

The steps of intervention of the liver tumour in Part I are summarised in Figure 4.

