12.2.1 Baseline evaluations

These will include radiological measurements of the FUS-targeted tumour and, where available, suitable control liver tumour(s) by Liver MRI/MR-Spectroscopy, Liver pCT and whole body FDG PET-CT. Only these selected liver tumours will be evaluated and followed-up for response. Control tumours will be selected based on their measurability at baseline and ideally be size-matched to the target tumour where possible. In some cases there may be no appropriate control tumours, in this case the only the target tumour will be evaluated.

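### MR-Spectroscopy endpoint 1b compares scans taken before and after drug and FUS together, so a significant rise cannot separate FUS-targeted delivery from preferential passive tumour uptake

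*Protocol*

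**What the plan says.** Tertiary objective 1 (section 3, Table 3) is to validate other ways of measuring uptake of doxorubicin in the tumour. For MR-Spectroscopy (1b), the endpoint is to indicate targeted delivery by "demonstrating a statistically significant increase in the tumour:background ratio of signal intensity following intervention compared to baseline". The synopsis words it the same way. Background is not defined.

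The timing and the design are fixed in the protocol:

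- Baseline scans, section 5.2: "Usually on d-1 but may be performed from day -7 to day 1 provided before intervention".
- Later scan, Table 3: "MRI/MR-Spectroscopy signal within 36 hours of intervention". A footnote to section 5.3 dates the intervention from the end of the final FUS exposure.
- Design, section 2: "All participants will receive ThermoDox® and FUS".

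A footnote to Table 3 allows the signal to come from metabolites or breakdown products. The heading above Table 3 limits these endpoints to participants in whom release has occurred.

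Non-FUS control tumours, which receive ThermoDox alone, are defined in Key Definitions. Section 12.2.1 provides for "radiological measurements of the FUS-targeted tumour and, where available, suitable control liver tumour(s) by Liver MRI/MR-Spectroscopy" at baseline. Endpoint 1b does not mention them.

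The synopsis (Study Design, Part I) says that targeted release will be determined from biopsies and blood samples "taken during intervention and/or using a radiological method (MR-Spectroscopy"), and Part II uses the same methods. Key Definitions also lets a participant be evaluable on biopsy or on radiology.

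**The concern.** Between the two scans two things change at once: systemic drug arrives and the tumour is heated. The null hypothesis actually tested is that drug, needle and heating together leave the ratio unchanged. It is not that FUS adds no drug to the tumour. Rejecting it supports uptake relative to background, but the endpoint labels the result targeted delivery.

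The protocol guards against this elsewhere. The two-fold limb of the primary endpoint refers to the Unreleased biopsy, of which section 5.4.2 says "ThermoDox® is circulating at this point, but not yet activated"; in Part II the Part I average takes its place. Plasma endpoint 1c uses time-matched clearance levels, fluorescence endpoint 1a a suitable control, and response endpoint 2 control tumours. Endpoint 1b has only the drug-free scan as its reference.

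At stake is whether a positive 1b could be reported as non-invasive evidence of FUS-triggered release, and whether MR-Spectroscopy could be declared a valid alternative for that purpose.

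**Working it through.** **Which exposures differ between the scans**

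| Measure | Reference | Later observation | What differs |
|---|---|---|---|
| Biopsy, two-fold limb (Part I) | After infusion, before final FUS | After final FUS | FUS (and elapsed time) |
| MR-Spectroscopy 1b | Before infusion and FUS | Within 36 hours after both | Drug, FUS, needle, time |

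No MR scan is scheduled between infusion and final FUS, so 1b has no equivalent of the Unreleased sample.

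**Illustration**

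The protocol gives no alpha, SD, effect size or power for 1b, so there is no figure to reproduce. Everything below except the maximum of 28 evaluable participants (section 16.1) is an assumption. The group-level test is also assumed.

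Let *r* be the fold change in the tumour:background ratio due to passive uptake alone, and *f* the fold change due to FUS. Take a paired t-test on ln(post ratio / baseline ratio), two-sided 5%, counting upward rejections only (nominal 2.5%). The noncentrality is ln(*r·f*)/SD × √n.

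Worked case: *f* = 1, *r* = 1.2, SD 0.3, n = 28. Then 0.182/0.3 × 5.29 = 3.22, against a critical value of 2.05 on 27 degrees of freedom. Upward rejection is 87.3%.

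Upward rejection with no FUS effect (*f* = 1):

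| n | SD | r=0.8 | r=0.9 | r=1.0 | r=1.1 | r=1.2 | r=1.3 |
|---|---|---|---|---|---|---|---|
| 10 | 0.3 | 0.0% | 0.2% | 2.5% | 14.5% | 40.4% | 69.3% |
| 14 | 0.3 | 0.0% | 0.1% | 2.5% | 19.6% | 55.7% | 85.6% |
| 28 | 0.3 | 0.0% | 0.0% | 2.5% | 36.7% | 87.3% | 99.4% |
| 10 | 0.5 | 0.1% | 0.5% | 2.5% | 7.8% | 17.7% | 31.7% |
| 14 | 0.5 | 0.0% | 0.4% | 2.5% | 9.7% | 24.3% | 44.4% |
| 28 | 0.5 | 0.0% | 0.1% | 2.5% | 16.2% | 46.0% | 76.3% |

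The test also responds to FUS. With *r* = 1 and *f* = 1.5, SD 0.3, rejection is 96.6% at n = 10 and 99.6% at n = 14.

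Masking: with *f* = 1.25 and *r* = 0.8, *r·f* = 1.00 and its logarithm is 0. Rejection is 2.5% at any n, although FUS works.

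**Target-minus-control contrast**

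Subtract the log change in the participant's own control tumour. If *r* is the same in both tumours it cancels. With SD 0.3 in each and independent changes, the SD of the difference is 0.3 × √2 = 0.424. In 40,000 simulated trials per setting with *f* = 1, upward rejection was 2.3% to 2.5% for n = 10, 14 and 28 and *r* = 0.8, 1.0, 1.2 and 1.5. Calculated power at n = 10, 14 and 28 is 76.7%, 91.0% and 99.8% for *f* = 1.5, and 31.8%, 44.5% and 76.5% for *f* = 1.25. Here n counts only participants with a usable control tumour.

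**The case against.** The endpoint is exploratory, restricted to participants with release, and serves an objective about measuring uptake, for which a pre-drug scan is a legitimate reference. The primary endpoint is quantified from biopsies and does not use 1b. All of this stands and keeps the point minor. It does not remove the point: release in a participant does not show that the rise on MR came from it, and the endpoint claims targeting, not just uptake.

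The denominator offers some protection. Systemic drug reaches the background too, and equal uptake cancels. Section 9.6 says that the liver metabolises doxorubicin extensively; if the background is liver and metabolites count, the ratio could fall. This also stands, and is why no direction of bias can be claimed.

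A reader might infer that the test detects passive uptake and not FUS delivery, or that a positive result shows only that doxorubicin was given. The documents support neither. The test responds to both sources, and a passive rise needs the tumour to gain more signal than the background.

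The control-tumour contrast is imperfect. Needle, biopsy and heating effects occur only in the target tumour and remain in the difference. Controls may be absent and are size-matched only where possible. Section 12.2 ties follow-up of tumours to the section 5.3 scans (days 12 to 60), so reading control-tumour spectroscopy at the 36-hour scan is not expressly provided for.

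**Conclusion.** The concern holds as a minor one. Endpoint 1b as fixed cannot distinguish FUS-targeted delivery from preferential passive uptake of systemic drug or its metabolites, and it can miss a real FUS effect if the background gains more signal than the tumour. This follows from the scan timing and the single-arm design and needs no numerical assumption.

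The size does depend on assumptions. In the illustration, rejection without any FUS effect runs from about 0% to 99%, according to the assumed passive change, SD and number of participants. Those figures show sensitivity and are not estimates for this trial.

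The practical weight comes from the synopsis wording on biopsy and/or MR-Spectroscopy and from the radiological route in the evaluability definition. Neither makes 1b the primary test, but neither should let 1b alone establish targeted release.

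**What to change.** 1. Define background for the tumour:background ratio.
2. State that the change from baseline in the target tumour alone shows uptake and is not evidence of targeted delivery.
3. Where a non-FUS control tumour lies in the field of both the baseline and the 36-hour scan, take as evidence for targeting the change in the target tumour minus the change in the participant's own control tumour. Otherwise report the target-tumour change descriptively.
4. Confirm in the protocol that control-tumour spectroscopy is read at the 36-hour scan.
5. Clarify in the synopsis and Key Definitions that endpoint 1b alone does not establish targeted release.

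The cost is mostly wording and analysis, provided item 4 can be met from the scans already planned. Fewer participants will contribute to the contrast, and the protocol does not say how many will have a control tumour. Local needle and heating effects stay in the difference and should be named as a limitation.

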¹⁰ During the Ultrasound Session feasibility of intervention is confirmed and a target tumour will be selected by ultrasound. Only one screening ultrasound is required.

¹¹ MRI includes the abdomen. Measurements made using the modified RECIST 1.1 criteria.

¹² Liver MRI includes the abdomen. The first Liver MRI/MR Spectroscopy following intervention can alternatively be performed on the same day as intervention, if intervention is in the morning. It should occur within 36 hours of the completion of intervention, and ideally within 24 hours where possible.

¹³ Liver pCT includes the abdomen. Measurements made using CHOI and the modified RECIST 1.1 criteria.

¹⁴ Three blood samples for pharmacokinetics in both Phases I and II (Pre-Treatment, Unreleased drug, Released drug).

¹⁵ Three biopsies in Part I (Pre-Treatment, Unreleased drug, Released drug), two biopsies in Part II (Released drug).

KEY DEFINITIONS

“Intervention” refers to attempted targeted release of ThermoDox® by mild hyperthermia using a focused ultrasound.

The “FUS-targeted tumour” or “target tumour” refers to the liver tumour treated with FUS following ThermoDox® delivery. This is in contrast to the RECIST definition, which defines target tumours as those measurable lesions which are followed through the patient’s treatment course.

A “non-FUS control tumour” refers to a liver tumour receiving ThermoDox® alone which has been selected for radiological follow-up and comparison with the target tumour.

The “desired range of mild hyperthermia” is used in the context of ThermoDox® release in this study and is defined as achieved bulk tissue temperature in the range of 41-47°C

“Optimal FUS exposure parameters” are defined as those combinations of settings on the HIFU device (power, duty cycle and transducer motion plan) which result in an adequate temperature rise to successfully release doxorubicin from the LTSls in the target tumour, without causing direct thermal tissue damage.

An “evaluable participant” is defined as a participant who has received FUS following delivery of ThermoDox® in Part I or II, and for whom it has been possible to evaluate the outcome of the intervention based on biopsy samples, or radiologically.

An “evaluable sample” is defined as a sample for which sufficient material was available for analysis and the analytical technique has provided quantifiable data.

ABBREVIATIONS

AE	Adverse Event
ADL	Activities of Daily Living
ADR	Adverse Drug Reaction

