3 OBJECTIVES AND ENDPOINTS

The objectives and endpoints for the study are detailed in the following tables. Only evaluable samples will be included in endpoint analysis. All endpoints will be evaluated at the end of Phase II.

The following qualifiers (*, †, ‡ and §) apply to Table 1, Table 2 and Table 3:

* In Part II the Unreleased biopsy is not performed and therefore the average value for all evaluable tumours receiving intervention in Part I is used as a comparison for the two-fold increase from Unreleased to Released biopsy.

† Duration refers to the completion of sample processing but not necessarily the sample analysis. The sample may be stored in a fixed or frozen state and analysed at some time period beyond the specified duration, for example to facilitate batch processing.

‡ Analytical method will only be performed where tissue mass allows. It is expected at most one technique can be performed in addition to the primary endpoint for a given sample. Where biopsy mass falls short, the primary endpoint will be prioritised.

§ Must be shown in at least 50% of evaluable participants.

Primary Objective	Primary Endpoint	How and when data is captured
To determine whether targeted release of doxorubicin from ThermoDox® ('drug') using mild hyperthermia generated non-invasively by focused ultrasound (FUS) is feasible in cancer patients	A demonstrable two-fold increase in*, or value exceeding 10µg/g of, the concentration of intra-tumoural doxorubicin at the treated tumour site following FUS-induced mild hyperthermia § Quantification of intra-tumoural drug release will be achieved by direct analysis of the intra-tumoural biopsy samples using standardised curve(s)	Analytical chemistry performed on a recorded mass of biopsy sample processed within 12 hours of intervention†

Table 1: Primary Objective and Endpoints for the TARDOX Study

Secondary Objectives	Secondary Endpoints	How and when data is captured
Part I only: To determine optimal FUS exposure parameters for a range of participant Body Mass Indices (BMIs) and tumour locations within the liver	Achievement of the desired range of mild hyperthermia in the target tissue as monitored by the implanted thermometry device during FUS exposure	Real-time thermometry monitoring during intervention

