2. To determine whether the dose of doxorubicin released has a therapeutically significant effect on the target tumour	Radiological evidence of tumour response at timepoints over 30 up to 60 days in the FUS-targeted tumour and control(s), as assessed by principles of Choi and RECIST response evaluation using MRI and CT [11, 12] and SUV _{max} using PET-CT [13] §	Scans to be performed within 60 days of intervention.

Table 3: Tertiary (Exploratory) Objectives and Endpoints for Parts I & II of the TARDOX Study

¹⁶ In some necrotic tumours, base line necrosis may be high (e.g. >30%) even prior to treatment. Consequently an increase in necrosis by no more than 25% over that of a suitable control can be used as an alternative endpoint.

¹⁷ The spectroscopy signal analysed may not be doxorubicin itself; metabolites or breakdown products of ThermoDox® may be utilized.

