16 STATISTICAL CONSIDERATIONS

16.1 Sample size and power

Evaluable participants will be recruited to either Part I or Part II of the study, up to a maximum of 28 evaluable participants overall. Non-evaluable participants will be replaced (section 6.1).

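### Footnote 16's alternative necrosis margin has no stated scale and, on either scale, cannot be failed in very necrotic tumours

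*Protocol*

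**What the plan says.** In the protocol, section 3, Table 2, the objective is "To assess the safety of FUS-induced mild hyperthermia for drug delivery". Its first endpoint is met by a persisting viability stain or by "percentage of cell or tissue necrosis under 30% following FUS exposure". Qualifier § applies to that endpoint: "Must be shown in at least 50% of evaluable participants". Qualifier ‡ also applies. It makes the analysis conditional on enough tissue and expects at most one technique beyond the primary assay per sample. FUS-related adverse events to 30 days are the second endpoint for the same objective.

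Footnote 16 qualifies the 30% limit: "In some necrotic tumours, base line necrosis may be high (e.g. >30%) even prior to treatment". It continues: "Consequently an increase in necrosis by no more than 25% over that of a suitable control can be used as an alternative endpoint". The protocol states no scale for the 25%, does not identify the control, and does not say what happens when the limit approaches 100%. The synopsis repeats the 30% rule without this alternative.

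The Key Definitions show what the criterion should protect against. Optimal exposure parameters are those "which result in an adequate temperature rise to successfully release doxorubicin from the LTSls in the target tumour, without causing direct thermal tissue damage".

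**The concern.** A no-worse-than margin has to give one answer for one biopsy, and it has to be possible to fail it. Footnote 16 is doubtful on both counts. A 25% increase in a quantity already measured in percent can mean 1.25 times the control value or the control value plus 25 points. Adding a fixed allowance to a bounded quantity also leaves less and less room to fail as the control value rises.

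At stake is the tissue-level part of the FUS safety conclusion. A participant who lost all remaining viable tumour tissue at the biopsy site could be counted among those showing no important thermal damage. Two analysts could also score the same pair of biopsies differently and both be following the protocol.

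**Working it through.** The plan gives no calculation for this margin, so there is no figure to reproduce. The check is arithmetic on the pass limit.

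**Inputs.** Main limit 30% (Table 2); margin 25% over control and trigger of high baseline necrosis, with above 30% given as an example (footnote 16); required share of participants 50% (qualifier §); cap on numbers "up to a maximum of 28 evaluable participants overall" (section 16.1). The control necrosis values *c* below are illustrative; the protocol gives no distribution.

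**Formulas.** Highest post-FUS necrosis that still passes:
- relative reading: L = min(100, 1.25c)
- percentage-point reading: L = min(100, c + 25)

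Share of remaining viable tissue that may be lost with a pass: (L − c)/(100 − c).

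| Control c | Limit, relative | Limit, points | Gap | Viable tissue lost, relative | Viable tissue lost, points |
|---|---|---|---|---|---|
| 30% | 37.5% | 55% | 17.5 | 11% | 36% |
| 40% | 50% | 65% | 15 | 17% | 42% |
| 50% | 62.5% | 75% | 12.5 | 25% | 50% |
| 60% | 75% | 85% | 10 | 38% | 62% |
| 70% | 87.5% | 95% | 7.5 | 58% | 83% |
| 75% | 93.75% | 100% | 6.25 | 75% | 100% |
| 80% | 100% | 100% | 0 | 100% | 100% |

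**Defect 1, scale.** Up to c = 75 the gap is (c + 25) − 1.25c = 25 − 0.25c points. It then shrinks to zero at c = 80. A tumour going from 40% to 60% necrosis fails the relative limit of 50% and passes the points limit of 65%.

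**Defect 2, ceiling.** The criterion cannot be failed once L = 100. Solving 1.25c = 100 gives c = 80; solving c + 25 = 100 gives c = 75. From 75% to just under 80% complete necrosis passes only in points; from 80% it passes on both readings. Stating a scale therefore cures defect 1 but not defect 2.

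**Effect on the 50% rule.** As an illustration, suppose all 28 participants are evaluable for this criterion and one of the passes is automatic. Then 14/28 = 50.0% meets the rule. With that participant set aside, 13/27 = 48.1% does not. The effect is decisive only near the boundary.

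**Is there a control biopsy?** Sections 5.2 and 5.4.2 give Part I a Pre-Treatment, an Unreleased and a Released biopsy. Part II has Released biopsies only, with nothing taken before the intervention and none from the control tumour. Qualifier * in section 3 supplies a Part I average as the Part II comparison for doxorubicin concentration; there is no equivalent for necrosis. In Part II, then, neither the trigger nor the comparator has a biopsy source in the same participant.

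**The case against.** The case for leaving this alone has four parts.

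- **Limited weight.** This is one component of a secondary endpoint. It can also be met by stain persistence, it is assessed only when there is enough tissue, and FUS-related adverse events inform the same objective. Part I has real-time thermometry as well. No test or sample size depends on the margin. All of this stands and limits the consequence.
- **Analysis-plan detail.** Sections 17 and 17.5 refer to a statistical analysis plan that is not at hand and could state the scale. This stands only in part. The margin is an endpoint definition that the protocol itself sets, and its wording permits opposite verdicts on one biopsy. The ceiling follows from the rule as written on either scale, so it is not a missing detail.
- **Unknown frequency.** The protocol does not say how many tumours have control necrosis of 75% to 80% or more. This stands.
- **A simple repair would misfire.** Tying everything to the participant's own Pre-Treatment biopsy cannot work in Part II. Choosing percentage points would adopt the looser scale, which also reaches the ceiling sooner. Both points stand and shape the fix.

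A reader might also infer that a tumour with little baseline necrosis, having failed the 30% limit, could be re-scored on the more lenient alternative. The text does not support that. Footnote 16 introduces the alternative as a consequence of high baseline necrosis, and although its cut-off is only an example, a tumour with low necrosis is not of that kind.

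**Conclusion.** Both defects hold. The unstated scale moves the pass limit by 17.5 points at control necrosis of 30%, 15 at 40% and 10 at 60%, so the verdict on the same biopsies can reverse anywhere from about 30% to just under 80%. Separately, the criterion cannot be failed from 80% (relative) or 75% (points), and complete loss of the remaining viable tissue is then scored as a pass.

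A reader might infer that choice of scale explains every undeserved pass. It does not: at 80% and above the two readings agree, and the cause is the 100% ceiling. Nor do the documents support the inference that the trial's safety conclusion as a whole fails, given the other evidence on the same objective and the 50% rule.

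The conclusion rests on taking the 25% as either a multiple of the control value or points added to it, the two natural readings. How often the ceiling would apply is unknown. The result is a real but modest fault in a secondary safety criterion, and it is cheap to correct.

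**What to change.** Amend footnote 16 before any biopsy is read for necrosis:

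1. **Scale.** State one. Prefer the stricter relative reading, or a limit on the share of remaining viable tissue lost. The second form, L = c + s(100 − c) with s below 1 fixed in advance, stays under 100% for any control value below 100% and so removes the ceiling as well.
2. **Trigger.** Apply the alternative only where a control biopsy shows more than 30% necrosis; otherwise the 30% limit applies.
3. **Control.** Name it for each Part. In Part I use the participant's own Pre-Treatment or Unreleased biopsy, and say which. Under section 5.4.2 the Unreleased biopsy follows the first FUS exposure unless that step is omitted, so it is not always an unheated baseline. In Part II either name another comparator, or state that the alternative is unavailable and list Released samples at or above 30% as of unknown baseline.
4. **Ceiling.** List tumours whose control value puts the limit at 100% as not evaluable for this criterion; do not count them as passes.

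Carry the same wording into the synopsis and the analysis plan. The cost is a few lines and a smaller denominator for this secondary endpoint, possibly including some Part II participants. Part I may also lose some, because limited tissue can leave no necrosis reading on the control biopsy.
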